1.1 Synopsis

Protocol Title: Randomized Crossover Study to Compare Effectiveness of a Device Providing Pressure Drops During Inspiration (TPAP) to Continuous Positive Airway Pressure in Obstructive Sleep Apnea

Protocol Name/Number: TheraPAP Equivalence

Sponsor: SleepRes, PLLC

Rationale: TheraPAP is a prototype device (with full documented electrical and isolation safety) being developed by SleepRes for the treatment of obstructive sleep apnea (OSA) that can deliver either standard CPAP at a set pressure or what is called TPAP¹. TPAP is a pressure control algorithm that lowers the pressure from the set pressure at the beginning of inspiration and does not return the pressure to the full set level until about halfway through expiration. The present study, TheraPAP Equivalence, is a crossover study designed to examine the efficacy and safety of TPAP vs. CPAP alone in the treatment of OSA.

Overall Design:

The TheraPAP Equivalence Study is a randomized, controlled, crossover study in participants with OSA. A split-night polysomnogram (PSG) will be conducted on CPAP and TPAP (approximately 3.5 hr. each treatment arm) in previously diagnosed OSA patients, to test the effectiveness of TPAP vs. CPAP. The sequence of periods for each participant are assigned in random order. Therapeutic CPAP level will be defined based on each individual's pressure levels from their currently used APAP device deemed to eliminate breathing obstructions for at least 90/95% of the sleep period (P90/P95) + 1 cmH₂O. P90/P95 will be defined based on the previous 2 months of adherent APAP usage (defined as averaging > 5 hours/night). On TPAP, the pressure drop during inspiration is generally done in two steps and varies, as outlined in table 1, based on the set pressure level, with larger drops occurring when the set pressure is higher. However, the pressure never goes below 5 cmH₂O. This lower pressure is returned to the set pressure level about halfway through expiration. These pressure drops are designed to make TPAP considerably more comfortable than CPAP.

¹ TPAP will be used herein to refer to the active treatment.

To assure that the participant is blinded to the therapy arm, all participants will start on CPAP and will be either left at CPAP or switched to TPAP after falling asleep, depending on the arm to which they have been assigned.

TPAP Pressure Drop values will be set according to the following table for (P90/P95) + 1 cmH₂O.

Adjusted P90/P95 cmH₂O Value	Pressure Drop 1 (cmH₂O)	Pressure Drop 2 (cmH₂O)
6.0 to 6.5	1	0
7.0 to 7.5	1	1
8.0 to 8.5	2	1
9.0 to 9.5	2	2
10.0 to 20.0	2	3

In the above chart, Pressure Drops 1 and 2 refer to the first and the second drops in pressure that occur during inspiration and are maintained until about halfway through expiration; P90/95 + 1 will be the set patient pressure for CPAP and TPAP during the study. To determine the Adjusted P90/P95 Value to get the correct Pressure Drops 1 & 2 settings:

- If the participant's machine-recorded P90/P95 is at a whole number, like 8.0, or a half pressure, like 8.5, add 1.0 cmH₂O to get the Adjusted P90/P95 Value.
- If the participant's machine-recorded P90/95 is *between* a whole number and a half number, round to the next half or whole number, then, add 1.0 cmH₂O to get the Adjusted P90/95 Value.
- Find the Adjusted P90/95 Value in the left column and then use the corresponding values for Pressure Drop 1 and Pressure Drop 2.

Key efficacy endpoints include the effect of TPAP on overall, non-rapid eye movement (NREM), REM, supine and lateral AHI, as well as sleep efficiency, sleep onset latency, sleep stage distribution, arousal index, total leak, and unintentional mask leaks vs. CPAP.

Number of Participants:

A total of 52 participants will be enrolled.

Study Duration:

The overall study duration for each participant will be up to two weeks including recruitment screening and one night in the lab.

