2.2.3 Biological Rationale

TPAP is an innovative device/algorithm designed to deliver a lower inspiratory than expiratory PAP. The drop in inspiratory pressure can be modulated during the inspiratory phase. Previous research has shown that reducing inspiratory PAP by placing a resistor in the inspiratory line can enhance subjective comfort and decrease leaks when compared to CPAP, despite maintaining a similar residual apnea-hypopnea index (AHI). However, the resistor could only provide a fixed inspiratory PAP reduction based on existing PAP settings. TPAP addresses this limitation by allowing for adjustable drops in inspiratory PAP throughout the inspiration phase, offering a potentially more personalized and adaptive therapeutic approach.

3 Endpoints

	Endpoints
Primary	
 • TPAP vs. CPAP AHI
Secondary	
 • TPAP vs. CPAP NREM and REM AHI⁴ • TPAP vs. CPAP NREM and REM AHI in supine and lateral position⁵ • TPAP vs. CPAP Sleep efficiency, sleep stage distribution, sleep onset latency, arousal index • TPAP vs. CPAP Unintentional mask leaks • Subjective preference of TPAP vs CPAP • Subjective sleep quality
Safety Endpoints⁶	
 • Spontaneous adverse events

4 Study Design

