4.1 Overall Design

The TheraPAP Equivalence Study is a randomized, controlled, crossover study in participants with OSA. Pre-screening is conducted to establish potential eligibility with a previous sleep study showing an AHI>10 events/hour, and a minimum of two months of adherent CPAP usage (defined as averaging > 5 hours/night). Eligible participants will undergo a split-night, in-laboratory polysomnogram (PSG) on CPAP and TPAP (3.5 hours for each treatment arm). The sequence of periods for each participant will be assigned in random order, although all participants will start on CPAP until asleep to blind them to the therapy arm. Therapeutic CPAP level will be defined based on each individual's pressure P95/P90 + 1 cmH₂O from the APAP

⁴ 10 minute per condition must be present for the endpoint to be considered.

⁵ 10 minute per condition must be present for the endpoint to be considered.

⁶ Although there will not be any direct treatment vs. control comparison here, we will assume that CPAP is safe and that any abnormal value recorded in the next morning compared to the evening before the polysomnography is due to treatment with TPAP.

device being used in the home over the previous two months. The drop in inspiratory PAP during the TPAP intervention arm will be based on the above P95/P90 according to Table 1.

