4.2.3 In-laboratory overnight PSG

The PSG will be conducted with a split-night design, i.e., approximately 3.5 hours on CPAP and 3.5 hours on TPAP, in random order. The switch between CPAP and TPAP will be operated through the interface screen on the TPAP device. During testing, no expiratory pressure relief will be used during CPAP regardless of such use during normal therapy at home. All patients will be asked to bring in the mask they normally use at night so that it can be used in the study, and the patients will be tested using two 1.8 m lengths of 22 mm tubing to prevent cross contamination. A commercial humidifier will be used to provide humidification since humidification is not supplied with the TheraPAP prototype.

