5.5 Measures to Minimize Bias

Each participant will begin the study in one of the treatment arms, (either CPAP or TPAP). The starting treatment arm is determined by a random number generator, as described in Section 7.2. All participants will start on CPAP until they fall asleep, then they will be switched to their designated therapy arm.

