6.1 Overnight study

- **Methods:** Standard overnight PSG recording, and data interpretation will be performed in accordance with the American Academy of Sleep Medicine (AASM) scoring manual. Participants will be instrumented with standard PSG electrodes and their usual at-home CPAP mask. This setup includes a finger pulse oximeter, chest and abdominal bands, EKG electrodes, a snore sensor on the neck, and anterior tibialis EMG electrodes. A manometer will be added between the end of the tube and the mask connecting tube to measure the participant's pressure directly, and its analog output will feed into the PSG device. The patient flow signal will be extracted from the flowmeter embedded in TheraPAP device filtering off the leak flow from total flow (output). This TheraPAP flowmeter data will be directed to the DC input on the polysomnogram, generating a real-time signal. This signal can be viewed in the control room. A panoramic of the setup in the patient room is shown in figure 2.

[figure not shown]

Figure 1. Continuous positive airway pressure (PAP)/TheraPAP circuit. TPAP, TheraPAP device. PSG, polysomnography.

Patients will report to the laboratory approximately two hours prior to their usual bedtime. Patients will be instructed not to drink alcohol or caffeinated beverages on the night of the

study. Time of lights out will be established according to the participant's approximate habitual bedtime. The participants will be given at least seven hours of time in bed (undergoing either CPAP or TPAP).

- Participants should be actively encouraged to spend at least 1/3 of the night in the supine position and at least 1/3 of the night in the lateral position on each night of study.
- Scoring: PSG studies will be scored for purposes of study endpoints by a registered PSG technician, blinded to treatment assignment.

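### Sleep onset latency is listed as a TPAP-versus-CPAP endpoint, but everyone falls asleep on CPAP, so under the usual definition it has no TPAP value

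*Combined protocol and SAP*

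**What the plan says.** **The start-on-CPAP rule.** Three places agree. The synopsis (Section 1.1, Overall Design) says that "all participants will start on CPAP and will be either left at CPAP or switched to TPAP after falling asleep". Section 4.1 describes a random order of periods, "although all participants will start on CPAP until asleep to blind them to the therapy arm". Section 5.5 says: "All participants will start on CPAP until they fall asleep, then they will be switched to their designated therapy arm". The stated purpose is to blind the participant.

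**The endpoint.** The synopsis names as key efficacy endpoints, among others, "sleep efficiency, sleep onset latency, sleep stage distribution, arousal index, total leak, and unintentional mask leaks vs. CPAP". The secondary list in Section 3 has "TPAP vs. CPAP Sleep efficiency, sleep stage distribution, sleep onset latency, arousal index".

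**The night.** On duration, the synopsis says: "The overall study duration for each participant will be up to two weeks including recruitment screening and one night in the lab". Section 4.2.3 says: "The PSG will be conducted with a split-night design, i.e., approximately 3.5 hours on CPAP and 3.5 hours on TPAP, in random order". The change of mode is made on the device screen. Section 6.1 sets a single lights-out at about the habitual bedtime ("Time of lights out will be established according to" that bedtime).

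**The analysis.** Section 7 covers sample size, randomization, analysis sets and interim analyses. It gives neither a definition nor an analysis of sleep onset latency.

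**The concern.** Sleep onset latency ends at the moment the participant falls asleep. Under the start-on-CPAP rule, TPAP cannot begin before that moment. The endpoint therefore asks for a treatment comparison over an interval in which only one treatment is ever given.

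The risk is a misleading report. TPAP is presented in the synopsis as more comfortable than CPAP, so readers may care whether people fall asleep as easily on it. A finding of no difference could be read as evidence that TPAP leaves sleep onset unaffected. A chance difference could be read as benefit or harm. Neither reading would be valid, because both groups fell asleep on CPAP.

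**Working it through.** The documents give no figure for sleep onset latency, so there is none to reproduce. The sample size of 52 (Section 7.1) was set for AHI and enters here only as a count.

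**Step 1. Trace the mode by sequence.**

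| Sequence (Section 7.2) | Mode from lights out to first sleep | Mode after first sleep | Mode after the mid-night switch |
|---|---|---|---|
| CPAP first | CPAP | CPAP | TPAP |
| TPAP first | CPAP | TPAP | CPAP |

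The second column is the same in both rows, and it is the only column that sleep onset latency measures under the definition assumed here (lights out to first sleep).

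**Step 2. Look for another chance to observe it.** There is one laboratory night, one split-night recording and one lights-out. Section 4.2.3 describes the switch only as an operation on the device screen. A phrase in Section 6.1 on body position could suggest more than one study night. It would not help, because the start-on-CPAP rule has no exception and any night would begin on CPAP.

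**Step 3. Try each possible contrast.** Let μC be mean latency on CPAP, μT the mean latency that would be seen on TPAP, and δ = μT − μC the effect the endpoint is meant to estimate.

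- *By mode delivered:* 52 planned values on CPAP, 0 on TPAP. The TPAP mean does not exist.
- *Within participant, as in a crossover:* this needs two latencies per person. Each person has one.
- *By assigned first arm:* D = mean(TPAP-first) − mean(CPAP-first). Both groups are observed on CPAP, so E(D) = μC − μC = 0 for every value of δ. The effect does not enter D, and more participants would not change that.

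**Step 4. Illustrate the third contrast.** Assume CPAP latencies follow a gamma distribution with mean 20 min and SD about 14 min, with 52 participants assigned at random and 4000 simulated trials per case. The latency distribution is an assumption, not a figure from the plan.

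| Assumed δ (min) | Mean of D (min) |
|---|---|
| 0 | −0.04 |
| −5 | −0.11 |
| −10 | −0.06 |
| −20 | −0.02 |

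The mean stays at about zero, as the algebra requires. The SD of D is about 4 min, in line with 14.1 × √(1/26 + 1/26) = 3.9 for equal groups. So under this assumption a difference of several minutes could appear by chance alone and be reported under a TPAP-versus-CPAP label.

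**The case against.** **The term is not defined.** The documents do not say that latency runs from lights out to first sleep, and Section 6.1 refers recording and interpretation to an external scoring manual. Section 4.2.3 does not say whether participants are asleep or awake at the mid-night switch. Section 3 also lists subjective preference between the two modes, which sits oddly with a participant who is never awake on TPAP. This objection stands in part, and the conclusion must be tied to the usual definition. A reader might infer that no latency on TPAP could be obtained under any definition. The documents do not support that: a return-to-sleep time after waking on TPAP could be measured in people who wake. It would be a different outcome, though, and nothing in the plan provides for it.

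**Starting on CPAP is a deliberate blinding choice.** That is so, and the rule is not criticised here. What needs correcting is an endpoint that does not fit it.

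**It is one item in a secondary list with no test or decision rule attached.** That limits the importance of the point, although the synopsis does call it key efficacy.

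**Two wider inferences are not supported.** A reader might conclude that sleep efficiency is biased towards TPAP because the wakeful start of the night is spent on CPAP. The plan does not say that this time is charged to CPAP as delivered. Sections 4.2.3, 5.5 and 7.2 speak of random-order periods and a starting arm or therapy. That language fits counting by assigned arm better, and counting by assigned arm has no expected bias. Section 5.5 can also be read as leaving the pre-sleep time outside both arms. So this is a missing detail, not a shown bias. Nor does anything here bear on the primary AHI comparison.

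**Conclusion.** The point holds in this form. With latency taken as lights out to first sleep, the plan yields 52 planned values on CPAP and none on TPAP, so the TPAP-versus-CPAP comparison in the synopsis and Section 3 has no TPAP side. Following the plan as written leaves only a between-participant contrast of CPAP with CPAP, whose expected value is zero whatever TPAP does.

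The conclusion rests on two things: the assumed definition, and the absence of any described awakening, second lights-out or second-period latency. The simulated figures are illustrative and the conclusion does not depend on them. One secondary endpoint is affected. It should be corrected before analysis.

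**What to change.** Remove sleep onset latency as a TPAP-versus-CPAP endpoint in the synopsis and in Section 3. Alternatively, report it once for all participants, descriptively, as latency on CPAP. If a latency after the mid-night switch is what is wanted, give it its own name and define its start, its end and who contributes a value.

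In the same edit, add one sentence saying to which arm, if either, the pre-sleep CPAP time is counted for sleep efficiency.

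The cost is wording in two places plus that sentence. Removal or descriptive reporting adds no procedure, and the blinding start on CPAP stays as it is. The plan loses one secondary comparison, which could not have been estimated in any case.

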1.2 Schedule of Activities (SoA)

Schedule of Activities

Procedures	Screening	Evening	Overnight	Morning
Telephone or outpatient contacts with participant	X			
Informed consent when patient comes to lab		X		
Analysis of CPAP compliance data		X		
Demographics		X		
Medical history & medications		X		
Height		X		
Weight		X		
Vitals ²		X		X
Randomization		X		
Pre-sleep questionnaire ³		X		
PSG Exam			X	
AE/SAE monitoring			X	X
Post-sleep questionnaire				X

Abbreviations: AE = adverse event; ESS = Epworth Sleepiness Scale; PSG = polysomnography; SAE = serious adverse event.

² Vital signs include the following: one measurement of seated blood pressure, pulse, respiratory rate.

³ Pre-sleep questionnaire includes recent sleep history for the last 2-3 nights, medications, caffeinated beverages, and alcohol consumption.

2 Introduction

2.1 Study Rationale

A device able to provide inspiratory positive airway pressure (PAP) < expiratory PAP, designated TPAP, is being developed by SleepRes for the treatment of obstructive sleep apnea (OSA). In prior studies, the administration of higher inspiratory than expiratory PAP did not substantially increase treatment efficacy or adherence to continuous PAP (CPAP), which remains low. In our recent investigation, we demonstrated that the addition of a resistor to the CPAP circuit to reduce inspiratory PAP increased subjective comfort. The present study, TheraPAP Equivalence, is a Crossover study designed to examine whether TPAP is equivalent to CPAP in the treatment of OSA.

2.2 Background

2.2.1 Obstructive Sleep Apnea

The National Commission on Sleep Disorders Research identified sleep disorders as a major public health burden. OSA is the most common of the more serious sleep disorders and affects approximately 20 million people in the United States (US), with approximately 13% of men and 6% of women affected (1). OSA is characterized by repetitive collapse or ‘obstruction’ of the pharyngeal airway during sleep, manifesting as repetitive episodes of hypopnea (i.e., shallow breathing) or apnea (i.e., paused breathing). These episodes of hypopnea or apnea may lead to hypoxemia, arousal from sleep, sleep fragmentation, excessive daytime sleepiness, and/or neuropsychological impairment.

Long-term, OSA is associated with increased mortality and a number of adverse cardiovascular, neurocognitive, metabolic, and daytime functioning consequences (2-11).

2.2.2 Unmet Medical Need

The large majority of OSA patients are treated with positive airway pressure, the most common of which is CPAP, provided by a machine that mechanically maintains an open airway. However, long-term adherence to therapy remains a challenge for many patients (12, 13). Common complaints include inconvenience, lack of perceived benefit, discomfort related to improper fitting of the interface, and difficulty expiring against positive pressure (14, 15).

As many patients cannot use CPAP because they find it intolerable, this represents a significant health concern, as OSA is associated with numerous adverse health outcomes and increased mortality. Strategies to improve tolerance of CPAP, and subsequently adherence, are needed.

2.2.3 Biological Rationale

TPAP is an innovative device/algorithm designed to deliver a lower inspiratory than expiratory PAP. The drop in inspiratory pressure can be modulated during the inspiratory phase. Previous research has shown that reducing inspiratory PAP by placing a resistor in the inspiratory line can enhance subjective comfort and decrease leaks when compared to CPAP, despite maintaining a similar residual apnea-hypopnea index (AHI). However, the resistor could only provide a fixed inspiratory PAP reduction based on existing PAP settings. TPAP addresses this limitation by allowing for adjustable drops in inspiratory PAP throughout the inspiration phase, offering a potentially more personalized and adaptive therapeutic approach.

3 Endpoints

	Endpoints
Primary	
 • TPAP vs. CPAP AHI
Secondary	
 • TPAP vs. CPAP NREM and REM AHI⁴ • TPAP vs. CPAP NREM and REM AHI in supine and lateral position⁵ • TPAP vs. CPAP Sleep efficiency, sleep stage distribution, sleep onset latency, arousal index • TPAP vs. CPAP Unintentional mask leaks • Subjective preference of TPAP vs CPAP • Subjective sleep quality
Safety Endpoints⁶	
 • Spontaneous adverse events

4 Study Design

4.1 Overall Design

The TheraPAP Equivalence Study is a randomized, controlled, crossover study in participants with OSA. Pre-screening is conducted to establish potential eligibility with a previous sleep study showing an AHI>10 events/hour, and a minimum of two months of adherent CPAP usage (defined as averaging > 5 hours/night). Eligible participants will undergo a split-night, in-laboratory polysomnogram (PSG) on CPAP and TPAP (3.5 hours for each treatment arm). The sequence of periods for each participant will be assigned in random order, although all participants will start on CPAP until asleep to blind them to the therapy arm. Therapeutic CPAP level will be defined based on each individual's pressure P95/P90 + 1 cmH₂O from the APAP

⁴ 10 minute per condition must be present for the endpoint to be considered.

⁵ 10 minute per condition must be present for the endpoint to be considered.

⁶ Although there will not be any direct treatment vs. control comparison here, we will assume that CPAP is safe and that any abnormal value recorded in the next morning compared to the evening before the polysomnography is due to treatment with TPAP.

device being used in the home over the previous two months. The drop in inspiratory PAP during the TPAP intervention arm will be based on the above P95/P90 according to Table 1.

4.2 Detailed Design

4.2.1 Pre-Screening

Recruiting for the TheraPAP Equivalence study will use an advertisement and a pre-screening checklist. The advertisement will be an email sent by Sleep Centers of Middle Tennessee (SCMT) to all of its patients inquiring about their interest in participating in the study. The email will provide interested patients with a link to an online form that they complete by adding their name and contact information. After they submit the form, they will be contacted by the study coordinator, who will discuss the study with them. Participants selected for eligibility will have a previous history of OSA of a severity consistent with enrollment criteria, have enough CPAP usage in the previous two months, and meet all other inclusion and exclusion criteria.

